4. DEVICES USED IN THE STUDY

a. Investigational Devices (Including Commercial Devices Used Off-Label)

Investigational Device 1	
Name:	N/A

b. IDE-Exempt Devices

IND-Exempt Device 1	
Name:	NIRScout

Description: The device is a portable NIRS recording unit. NIRS technology uses specific wavelengths of light, introduced at the scalp to enable the non-invasive measurement of changes in the relative ratios of deoxygenated hemoglobin (deoxy-Hb) and oxygenated hemoglobin (oxy-Hb) in the capillary beds during brain activity.

5. PARTICIPANT POPULATION

a. Planned Enrollment

135 participants between 7 and 18 years of age and 135 caregivers (one caregiver for each participant). Participants will be enrolled at SYS in Sacramento (not Stanford-affiliated) and at UCSF CAS in San Francisco (not Stanford-affiliated). These will be trauma exposed youth presenting with posttraumatic stress symptoms and their caregivers as this is the target population for CCT and TF-CBT.

b. Age, Gender, and Ethnic Background

Youth ages 7-18 will be recruited for the study of all genders and ethnic backgrounds.

c. Vulnerable Populations

This study involves vulnerable subjects as we aim to study the effectiveness of several interventions for traumatized youth. 135 youth will be under treatment with therapists trained in assessment and treatment of traumatized youth. They will evaluate participants to determine if they need additional resources. We will provide referrals to those resources and work closely with SYS and UCSF CAS to ensure they are provided and SYS and UCSF CAS also have additional supportive services to which participants may be referred. For those youth that are community-referred, our research staff and therapist will provide the participants with any appropriate resources necessary.

d. Rationale for Exclusion of Certain Populations

N/A

e. Stanford Populations

N/A

f. Healthy Volunteers

N/A

g. Recruitment Details

Potential participants will be identified by the therapists at SYS and by staff at UCSF CAS. A designated contact person at each site will verify that potential participants agree to be contacted for screening by the research coordinator/UCSF designated staff. The study coordinator/UCSF designated staff will only then conduct a phone or in-person interview with potential participants' legal guardians to assess inclusion/exclusion criteria. If qualified participants and their legal guardians consent, they will be enrolled in the study.

Potential participants may also be identified via responses to flyers posted in community centers and public forums. Additionally, flyers, letters, and supplemental informational guides will be sent to physicians/pediatricians, schools, and community organizations to distribute to any patients or students that may be identified as potential participants.

School staff will speak with parents of children they have identified as potential study candidates and with verbal consent will submit parent's name and phone number so that the Stanford University research coordinator can make contact directly to conduct phone screening. School staff may also obtain verbal consent for a Stanford research team member to come to the school site and do informed consent process and screening at school for any participants that may have transportation barriers.

h. Eligibility Criteria**i. Inclusion Criteria**

- 1) Report exposure to at least one traumatic event and endorse any symptoms on the UCLA PTSD Reaction Index
- 2) Ages 7-18
- 3) Willingness to participate in therapy and fNIRs imaging
- 4) Caregiver willing to participate in the study
- 5) Perpetrator of the traumatic event is not living in the home with the child

ii. Exclusion Criteria

- 1) Low cognitive functioning (IQ less than 70)
- 2) Substance dependence as defined by DSM criteria
- 3) Autism/Schizophrenia
- 4) Clinically significant medical illness

i. Screening Procedures

Participants will be referred by therapists at SYS and by a designated staff member at UCSF CAS to be recruited for the study. 135 participants will be enrolled by Stanford research staff. The research coordinator/designated UCSF staff will contact caregivers of potential participants to conduct a phone or in-person screening to go over inclusion/exclusion criteria. Participants and their caregivers that qualify and provide consent will be enrolled in the study.

A letter will also be sent to physicians, pediatricians, and other clinicians in hospitals and clinics asking them to refer any patients that may be potential participants. Flyers will also be distributed in community organizations, youth centers, schools, and other community public spaces.

School staff will speak with parents of children they have identified as potential study candidates and with verbal consent will submit parent's name and phone number so that the research coordinator can make contact directly to conduct phone screening. School staff may also obtain verbal consent for a Stanford research team member to come to the school site and do informed consent process and screening at school for any participants that may have transportation barriers.

j. Participation in Multiple Protocols

We will ask participants if they are enrolled in other studies. Participants may enroll in more than one study.

k. Payments to Participants

Participants who complete all behavioral assessments and fNIRs at each time phase will receive a \$25 gift card (a total of \$100) which will incentivize participants to complete the assessments.

l. Costs to Participants

There are no costs to the participant.

m. Planned Duration of the Study

The entire duration of the study will be 4.5 years ending in July 2020.

- (i) 10-15 minutes for screening of participants
- (ii) 15-18 weekly 45-minute treatment sessions over the duration of 3 months. There will be completion of 3 hour behavioral assessments over 4 time points (pre-, mid-, post-treatment and six month follow-up). Participants will also do 45-60 minutes of fNIRs imaging at each of the time points.
- (iii) Participant data will be processed and analyzed per participant, but mostly in bulk. Participant data will be analyzed periodically throughout the length of the study. After data acquisition, data will be checked for quality and will be double-entered. Analysis will be within and between groups.

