2. STUDY PROCEDURES

a. Procedures

The children will be referred from Stanford Youth Solutions and UCSF CAS. UCSF has approved recruitment at their site and they have provided their own consent forms. Some children may also be self-referred from the community as a response to a flyer that may have been distributed to them in a public forum, from a community organization, from a physician/pediatrician, or a hospital setting.

School staff will speak with parents of children they have identified as potential study candidates and with verbal consent will submit parent's name and phone number so that the research coordinator can make contact directly to conduct phone screening. School staff may also obtain verbal consent for a Stanford research team member to come to the school site and do informed consent process and screening at school for any participants that may have

transportation barriers.

Caregivers will undergo a telephone or in-person screening according to the inclusion and exclusion criteria. Written consent for participation will be obtained from participants, parents and/or legal guardians. Participants will be randomly assigned to one of three treatment conditions: TF-CBT, CCT, or TAU. Assessments will be administered at 4 time points: 1) pre-treatment, 2) mid-therapy, 3)post-treatment, and 4) three month follow-up. A medical/developmental history form will be completed only pre-treatment. The vocabulary and block design subtests of the Wechsler Abbreviated Scale of Intelligence (WASI-II) will be administered only pre-treatment to rule out potential confounds for neuroimaging. The UCLA PTSD Reaction Index (PTSD-RI) parent and child versions will be used to assess exposure to traumatic events and posttraumatic stress symptoms. Given that trauma has high comorbidity with depression and anxiety disorders these symptoms will be assessed using the Multidimensional Anxiety Scale for Children (MASC), Children's Depression Inventory (CDI), and Trauma Symptom Checklist for Children (TSCC) or Trauma Symptom Checklist for Young Children (TSCYC). Executive functioning will be assessed by both child and parent report using the Behavioral Rating Inventory of Executive Function (BRIEF) and the Brief Impairment Scale (BIS) for the parent. A post-treatment services form will be completed only at the three month follow up appointment.

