b. International Research Risk Procedures

N/A

c. Procedures to Minimize Risk

Confidentiality will be maintained by using designated therapy rooms at SYS (including for community-referred youth) and UCSF CAS and assigning participants a coded number by which all their data will be identified.

For school-referred youth, therapy may be provided at their respective school site in designated rooms for confidential therapy sessions. These rooms are already being used by school psychologists and social workers and will be made available for us to minimize any potential transportation barriers for participants.

Evaluation of the participants will occur at three time points during the treatment and if any hazards are detected such as co-morbid psychological symptoms, the study therapists will provide appropriate referrals to community resources.

d. Study Conclusion

The study will terminate in July 2020, after all 135 participants have completed treatment.

Regular evaluations during four time points (pre-, mid-, post- treatment, and 3 month follow-up) will facilitate identification of any adverse effects. If participants have clinically significant worsening of PTSD, anxiety, or depressive symptoms, suicidal or violent behaviors, or substance dependence therapy will be discontinued. The study therapists, all masters level clinicians, will be able to make community referrals if they determine further intervention is warranted. Adverse effects and specific stopping triggers will be reported to the IRB.

e. Data Safety Monitoring Plan (DSMC)

i. Data and/or events subject to review

N/A

ii. Person(s) responsible for Data and Safety Monitoring

N/A

iii. Frequency of DSMB meetings

N/A

iv. Specific triggers or stopping rules

N/A

v. DSMB Reporting

N/A

vi. Will the Protocol Director be the only monitoring entity? (Y/N)

Yes.

vii. Will a board, committee, or safety monitor be responsible for study monitoring? (Y/N)

No.

f. Risks to Special Populations

Research not involving greater than minimal risk. The research must present no greater than minimal risk to children and adequate provisions must be made for soliciting the assent of the children and the permission of their parents or guardians. Please provide rationale for the above statement.

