# Child Characteristics, Neuromarkers, and Intervention Components Impacting Treatment Outcome: CCT, TF-CBT, TAU

NCT02926677

9/18/20

[name], Principal Investigator  
Stanford University  
Stanford, California 94305

Planned Sample Size: Analyses will be conducted on data for participants that completed treatment from baseline to month 3 (end of treatment). The sample size is 8 participants for the CCT group, 8 for TF-CBT, and 6 for TAU.

Planned Analyses: Factorial ANOVAs comparing baseline to month 3 (end of treatment) total scores on all outcome measures (UCLA PTSD Reaction Index for DSM 5 child and parent versions, Child Depression Inventory, Multidimensional Anxiety Scale for Children, Behavior Rating Inventory of Executive Function) will be conducted for each treatment arm.

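### Do 15-18 weekly sessions in a 3-month treatment period, and a follow-up given as both three and six months, undermine the SAP's month 3 comparison?

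*Protocol*

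**What the plan says.** Section 5m of the Protocol describes "15-18 weekly 45-minute treatment sessions over the duration of 3 months". It goes on: "There will be completion of 3 hour behavioral assessments over 4 time points (pre-, mid-, post-treatment and six month follow-up").

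Section 2a gives a different time for the last of the four visits: "Assessments will be administered at 4 time points: 1) pre-treatment, 2) mid-therapy, 3)post-treatment, and 4) three month follow-up". It repeats that time for the services form: "A post-treatment services form will be completed only at the three month follow up appointment". Section 6d agrees with 2a: "Regular evaluations during four time points (pre-, mid-, post- treatment, and 3 month follow-up"). None of these places says what the three or six months are counted from.

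Section 5k ties payment to the visits: "Participants who complete all behavioral assessments and fNIRs at each time phase will receive a" $25 gift card, for a total of $100. Section 2g puts average active participation at 3 to 4 months per child.

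The SAP uses one time label twice. The analysis set is the participants who "completed treatment from baseline to month 3 (end of treatment"), and the analysis is "Factorial ANOVAs comparing baseline to month 3 (end of treatment) total scores on all outcome measures". It plans no analysis of the mid-treatment or follow-up visit.

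**The concern.** Two things look wrong.

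First, the session count in section 5m does not fit its own duration. A child seen weekly for even the minimum 15 sessions has not finished at calendar month 3, yet the SAP equates month 3 with the end of treatment for both the analysis set and the endpoint. If calendar month 3 governed, a child on the weekly schedule would either be measured before the last session or fail to count as a completer. With 8, 8 and 6 children analysed, reclassifying one child changes an arm by 1/8 = 12.5% or 1/6 = 16.7%. If the last session governed, time from baseline would differ between children.

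Second, the fourth visit has two stated times and no stated starting point. A reader could not tell when follow-up data were due.

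**Working it through.** **Inputs.** 15-18 sessions, weekly, 3 months (Protocol 5m); follow-up at three months (2a, 6d) or six months (5m); active participation of 3 to 4 months (2g); $25 per time phase and $100 in total (5k). One month is taken as 365.25/12 = 30.44 days. The first session is assumed to fall at baseline, with no missed sessions.

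**Stated duration.** 3 × 30.44 = 91.3 days, and 91.3/7 = 13.04 weeks. With sessions on days 0, 7, ..., 91, at most 14 weekly sessions fit, so 15-18 in 3 months is not reproduced.

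**Span of the course**, from first to last session, 7 × (s − 1) days:

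| Sessions | Days | Weeks | Months | Over 3 months |
|---|---|---|---|---|
| 15 | 98 | 14 | 98/30.44 = 3.2 | 98 − 91.3 = 6.7 days |
| 18 | 119 | 17 | 119/30.44 = 3.9 | 119 − 91.3 = 27.7 days |

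If each session is counted as a full week, the spans are 15 and 18 weeks (3.4 and 4.1 months), and the overruns are 1.96 and 4.96 weeks.

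**Comparison with section 2g.** The first-to-last span of 3.2-3.9 months lies inside 3 to 4 months, provided that active participation means the treatment period. The 3 months in 5m then reads as a rounded figure: close for 15 sessions, loose for 18.

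**What the SAP's time point refers to.** Sections 2a, 5m and 6d all name the third assessment post-treatment, and none of them schedules it by calendar date. The SAP limits the analysis to children who completed treatment and adds end of treatment in brackets after month 3. An endpoint taken before the last session would contradict both the visit's name and the completer restriction. The only support for a calendar reading is the label itself.

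**Number of visits.** $100/$25 = 4, which matches the four time points in every list. Three and six months are therefore two names for one visit, not two visits.

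**Starting point of the follow-up.** A visit three months from baseline falls at week 13.04, which is 0.96 to 3.96 weeks before the last session (weeks 14 to 17). It could not be a separate visit listed after post-treatment. Three months in 2a and 6d must therefore run from about the end of treatment.

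For six months in 5m there are two readings:

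- From baseline: 6 × 30.44/7 = 26.09 weeks. On the nominal 3-month course this is 26.09 − 13.04 = 13.04 weeks after treatment, the same as a three-month follow-up. On the weekly schedule it is 26.09 − 14 = 12.09 to 26.09 − 17 = 9.09 weeks after the last session, or 0.96 to 3.96 weeks short of three months.
- From end of treatment: the two stated times are 26.09 − 13.04 = 13.04 weeks apart.

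The documents do not say which applies. Neither reading alters the baseline to end-of-treatment comparison.

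**The case for a change.** The best case for acting is that the SAP relies on the label for both its analysis set and its endpoint, and that rounding does not excuse an overrun of nearly 4 weeks at 18 sessions. At calendar month 3 such a child has had at most 14 of 18 sessions, or 78%. The documents never state that six months runs from baseline, and that reading agrees exactly with the other sections only if treatment lasts exactly 3 months. The fourth visit also has uses of its own: it is one of the evaluations meant to identify adverse effects (6d), and the services form is completed only there (2a).

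Much of this stands. The arithmetic is right, the wording in 5m is loose at the upper end, and the starting point of the six months is unstated. The step to a consequence for the analysis does not stand. It needs the calendar reading, which conflicts with the visit's name and the completer restriction, and nothing in the documents shows that a child was assessed early or excluded. If the visit follows the last session, variation in elapsed time comes from allowing 15 to 18 sessions (17 − 14 = 3 weeks, before any missed sessions). It would be there however the duration was worded.

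**Conclusion.** The inconsistencies are real but clerical. Section 5m understates the span of its own weekly schedule by about 1 to 4 weeks (2 to 5 if full weeks are counted), and it gives the fourth visit a different time from sections 2a and 6d. Sections 2a, 2g, 5m and 6d and the SAP label must be reconciled as text, with one starting point for each interval. Which session count, duration or follow-up time is right is not for this review to say.

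No change to the statistical plan follows. Its only comparison is baseline against end of treatment in completers, and an analyst would take the post-treatment visit for it. The ANOVA, the outcome list and the group sizes of 8, 8 and 6 stay the same, and the follow-up visit is not part of the analysis. The SAP is dated 9/18/20, after the stated July 2020 end of the study, so new wording could not alter conduct. Giving the actual assessment times in the report would help a reader if the dates were kept, which the documents do not say.

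This conclusion rests on reading month 3 as the event-based visit and active participation in 2g as the treatment period. Records showing that the analysed assessments were fixed by calendar date would reopen the point.

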e. Alternative Procedures or Courses of Treatment

Other forms of psychotherapy or psychopharmacology may be advantageous to participants. However, there is no strong evidence to suggest that these treatments are necessarily better than the interventions that participants will be receiving.

f. Will it be possible to continue the more (most) appropriate therapy for the participant(s) after the conclusion of the study?

Yes.

g. Study Endpoint(s)

The study is scheduled to end by July 2020. On average, each individual will actively participate for three to four months. If one study intervention clearly proves to be more effective than another during the course of the study then the study will be terminated before the projected total number of participants has been enrolled and we will make that intervention available to all participants.

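### The only analysis plan supplied postdates the scheduled study end and reports achieved counts as planned, so its choices are not shown to be prespecified and its p-values cannot be read as confirmatory

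*Protocol*

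**What the plan says.** **Timing.** Protocol section 2.g says "The study is scheduled to end by July 2020". Section 5.m agrees: "The entire duration of the study will be 4.5 years ending in July 2020". Section 6.d ties that date to full recruitment: "The study will terminate in July 2020, after all 135 participants have completed treatment". The SAP carries one date, 9/18/20.

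**Counts.** Under its heading for planned sample size, the SAP limits the analysis to participants who completed treatment and states: "The sample size is 8 participants for the CCT group, 8 for TF-CBT, and 6 for TAU".

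**Looks at the data.** Protocol section 5.m(iii) says "Participant data will be analyzed periodically throughout the length of the study". A sentence on quality checks and double entry after data acquisition follows, and then "Analysis will be within and between groups". Section 2.g adds: "If one study intervention clearly proves to be more effective than another during the course of the study then the study will be terminated". In the monitoring section (6.e), the item "iv. Specific triggers or stopping rules" is answered N/A, and the Protocol Director is the only monitoring entity.

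**Measures.** Protocol section 2.a lists the PTSD-RI (child and parent), MASC, CDI, TSCC or TSCYC, BRIEF (child and parent) and BIS (parent). It sets four time points and adds fNIRS at each. The SAP lists the PTSD-RI (child and parent), CDI, MASC and BRIEF at baseline and month 3 only, analysed by factorial ANOVA, and describes this list as covering all the outcome measures.

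**The concern.** A p-value below 0.05 carries a 5% error rate only if the outcome, visit, analysis set and model were chosen without reference to the results. Usually a protocol or a dated SAP written before data access shows that. Here the protocol names no primary outcome, primary visit, analysis set or test; its section on study endpoints gives only an end date and a termination rule. The one document that makes these choices is dated after the scheduled end and already knows who completed in each arm.

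The SAP also narrows what the protocol set out to measure and gives no reason. Because it describes the shorter list as complete, someone reading it alone could not tell that two instruments, the imaging and two post-baseline visits are missing. The headings present the content as planned, so that reader would probably take the results as prespecified tests. At stake is the evidential status of the results. The small sample is a separate matter.

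**Working it through.** The documents give no alpha, power calculation or expected error rate, so there is no figure of the plan's own to reproduce. The check has three parts.

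**1. Dates and counts (from the documents)**
- From 31 July 2020 to 18 September 2020 is 49 days; from 1 July it is 79 days. The SAP date therefore falls 49 to 79 days after the scheduled end.
- Completers: 8 + 8 + 6 = 22. Against planned enrolment, 22/135 = 16.3%. Uneven counts this far below plan are achieved numbers. They show that completion by arm was known. They do not show that outcome scores were known.

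**2. What the SAP selects from the protocol**

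| Item | Protocol | SAP |
|---|---|---|
| Post-baseline visits | 3 (mid-therapy, post-treatment, follow-up) | 1 (month 3, end of treatment) |
| Behavioural instruments | 6 (PTSD-RI, MASC, CDI, TSCC/TSCYC, BRIEF, BIS) | 4 (drops TSCC/TSCYC and BIS) |
| Scores, counting informants | 8 (PTSD-RI ×2, MASC, CDI, TSCC/TSCYC, BRIEF ×2, BIS) | 5, or 6 if BRIEF child and parent are separate |
| Imaging | fNIRS at each time point | none |
| Analysis set | not stated | completers |
| Model | not stated | factorial ANOVA |

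Every SAP scale and both SAP visits already appear in the protocol. What first appears in the SAP is the selection among them, the completer set and the model.

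**3. How much free selection could matter (illustration)**

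Assumptions that are not in the documents: two-sided alpha 0.05, and k normal test statistics under the null with a common correlation r. The chance that at least one passes is

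P(any |z| > 1.96) = 1 − ∫ φ(x) [Φ((1.96 − √r·x)/√(1−r)) − Φ((−1.96 − √r·x)/√(1−r))]^k dx.

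- *Visit, best of k = 3:* 13.6% at r = 0.3, 11.8% at r = 0.6, 9.8% at r = 0.8.
- *Instruments:* at r = 0.5, four fixed tests give 15.6% and six give 20.7%. If four of six are chosen with the results in hand, the chosen set contains a significant test whenever any of the six is significant, so 20.7% applies. The part due to selection is 20.7 − 15.6 = 5.1 points. The other 15.6% is ordinary multiplicity among four listed tests, which a multiplicity rule would address. The 5.1 points arise before the list exists, so a rule applied only to the list cannot remove them.

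**The case against.** The strongest reply is that nothing here shows a choice driven by results. The SAP's scales and visits were all in the protocol, and end of treatment is a conventional time point. The SAP shows its date and completer counts openly, states no alpha and makes no explicit confirmatory claim. July 2020 is a scheduled end; no actual last-visit date is given. The documents do not say whether 9/18/20 is a first or a revised date, or whether an earlier SAP existed.

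All of that stands, and it limits what can be said. A reader might infer that the choices are post hoc and were made after between-group analyses had been run. The documents do not support that. The periodic analyses are a plan, not a recorded event. The sentence on between-group analysis is separate and follows the one on checks after data acquisition, so it need not describe the periodic work. The termination rule in section 2.g makes interim comparisons a reasonable expectation, because it cannot operate without them, but no look is reported.

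The reply does not establish prespecification. A confirmatory reading needs positive evidence that the choices preceded access to results, and the documents give none. They describe no separation between results and analysis decisions: the Protocol Director is the sole monitor, and no stopping boundary or number of looks is stated. Nor does the reply explain why a reduced list is described as complete.

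**Conclusion.** The point holds in this form: the SAP's analysis set, visit, scales and model are not shown to be prespecified, so its p-values cannot be read as confirmatory. This rests on the SAP date, the achieved counts given as planned, the unexplained narrowing of visits and instruments, and the absence of any earlier specification in the documents supplied.

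The size cannot be known, because it depends on whether and how results influenced the choices. Under the stated assumptions, free choice of visit would roughly double or nearly triple a nominal 5% (9.8% to 13.6%), and free choice of instruments would add about 5 points to existing multiplicity. It would be tempting to charge the whole 20.7% to selection, but most of it would be present with four tests fixed in advance. These figures show what unconstrained selection could do; they do not estimate what happened. An earlier dated SAP making the same choices before data access would answer the point.

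**What to change.** Unless an earlier dated SAP is supplied:

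1. Label the analyses exploratory in the SAP and in any report, and make no confirmatory claim.
2. Report estimates with 95% CIs for every protocol scale at every post-baseline visit (mid-therapy, post-treatment, follow-up). This adds TSCC/TSCYC and BIS and gives BRIEF child and parent separately: 8 scores × 3 visits = 24 rows per comparison. Choice of visit or scale then cannot drive the message.
3. Replace the description of the list as all outcome measures with the full protocol list, including fNIRS, or mark it as a subset.
4. State when the analysis set, visit, scales and model were chosen relative to data access, and whether any between-group comparison was done before then. If none was done, say so.

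In labelling the follow-up rows, reconcile the protocol's timing: sections 2.a and 6.d say three months, section 5.m says six.

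The cost is some SAP wording and one longer table, using assessments the protocol already schedules. The downside is that the results are presented as exploratory.
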